5. EQ-5D-5L
6. AVVQ
7. SF-36 (up to 12-month visit)
8. Patient reported outcomes:
 - a. VenousDQoL
 - b. Patient-reported symptoms (up to 12-month visit)
9. Adjunctive therapy assessment
10. AE assessment
11. Healthcare utilization since last study visit
12. VLU Study:
 - a. Active ulcers: ulcer assessment, ongoing wound care, photographs for core laboratory, healing status
 - b. Post-healing confirmation: recurrence status.

48, 60 months (+/-8 weeks)

Subjects will return to the site for follow-up to conduct the following assessments (limb-specific assessments are of the target limb only). Subjects may also complete 48 and 60 months visit remotely per physician's discretion if subjects cannot return to the site for follow-up.

1. DUS:
 - a. Areas of patency, if any
 - b. Reflux along treatment area
 - c. Evidence of thrombus
2. CEAP classification
3. rVCSS
4. EQ-5D-5L
5. AVVQ
6. Patient reported outcomes:
 - a. VenousDQoL
7. Adjunctive therapy assessment
8. AE assessment
9. Healthcare utilization since last study visit
10. VLU Study:
 - a. Active ulcers: ulcer assessment, ongoing wound care, healing status
 - b. Post-healing confirmation: recurrence status.

If remote visit occurs, the following assessments can be completed via telehealth and/or hard-copy of questionnaires required to be completed via mail. Questionnaires can be sent to subjects via mail and subjects can complete and return it back to the site via mail.

1. EQ-5D-5L
2. AVVQ
3. Patient reported outcomes:
 - a. VenousDQoL
4. AE assessment
5. Healthcare utilization since last study visit
6. VLU Study:
 - a. Active ulcers: ulcer assessment, ongoing wound care, healing status
 - b. Post-healing confirmation: recurrence status

10.11. Unscheduled Visits

A visit outside of the study follow-up schedule will be reported as unscheduled study visit if it was conducted for the evaluation of an AE per the AE reporting requirements in this study. In addition to any applicable AE treatment or diagnostic testing, the following additional assessments may be completed, per the treating physician's discretion (limb specific assessments are of the target limb only):

1. Required: AE assessment
2. CEAP classification
3. rVCSS
4. DUS.

10.12. Additional Follow-Up Visits: VLU Study Active Ulcers

2, 3, 4, 5 (+/- 7 days), 8, 10 Months (+/- 2 weeks) until Healing Verification

Ulcer assessments on the target limb will take place at standard study visits (Screening visit, Baseline visit, Day 7, Day 30, and 6, 12, 24, 36, 48 and 60 months). In addition, visits at 2, 3, 4, 5, 8, and 10 Months will be conducted for active ulcers, until healing has occurred and been verified. If complete healing has not occurred by 24 months, subjects will continue to follow standard wound care and remaining study visits. At these active ulcer visits, sites will conduct the following assessments:

1. Active ulcer assessment
2. Ongoing wound care
3. Ulcer-specific healthcare utilization
4. Photographs for core laboratory
5. Healing and/or recurrence assessment
6. AE assessment.

Ulcer Healing Verification Visit

Once the site research team has been informed of all wounds healing on the target ulceration by the wound care center, the subject will undergo an ulcer healing verification visit within 2 weeks of ulcer healing to confirm healing and collect photographs of the ulcer. The ulcer assessment core laboratory will verify healing. If core laboratory does not confirm healing with the first set of photographs, the subject will return in 1 week for additional photographs to be collected and sent to the core laboratory. If the core laboratory does not confirm healing after the second set of photographs, but the treating physician believes the ulcer has healed, the ulcer will be classified as healed. The ulcer healing verification visit may occur up to 24 months, after which core lab ulcer imaging for wound healing will not be required. Data will continue to be collected for healing and recurrence status changes through 60 months.

10.13. Assessment of Effectiveness

Procedure effectiveness will be measured as primary target vein and target vein closure, defined as DUS showing closure along the entire treated vein segment with no discrete segments of patency exceeding 5 cm after ETA or VenaSeal™ system treatment and absence of refluxing vein or residual vein after surgical stripping. It will also be measured as elimination of clinically relevant superficial truncal disease in target vein at the time of index procedure in addition to reintervention and time to reintervention of a target vein (including primary target vein) through 60 months (through 12 month visit for subjects randomized to the VenaSeal vs. Surgical Stripping Study) assessed at each follow-up visit (except 7 days) until reintervention occurs or the study ends.

Ulcer healing effectiveness will be measured by time to ulcer healing, percent area healing per month and absolute healing, as verified by the independent core laboratory.

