5.2.3 Secondary Endpoints

Data supporting the following endpoints will be collected for both the CEAP 2-5 Randomized Studies as well as the VLU Study. When appropriate, data will be evaluated for the CEAP 2-5 Randomized Studies to compare the VenaSeal™ system to surgical stripping or ETA. Data may also be pooled for all VenaSeal™ system subjects from the CEAP 2-5 Randomized Studies and VLU Study as appropriate. The surgical stripping data will be collected up to the 12 months' time point.

Effectiveness secondary endpoints

1. Anatomic closure of primary target vein at 30 days, and 12, 24, 36, 48 and 60 months:
 - For subjects treated with the VenaSeal™ system or ETA it is defined as DUS showing vein closure along the entire treated vein segment with no discrete segments of patency exceeding 5 cm.
 - For subjects treated with surgical stripping this is defined as absence of refluxing or residual vein and it will be collected at 30 days and 12 months only.
2. Anatomic closure of target vein at 30 days, and 6, 12, 24, 36, 48 and 60 months:
 - For subjects treated with the VenaSeal™ system or ETA this is defined as DUS showing vein closure along the entire treated vein segment with no discrete segments of patency exceeding 5 cm.
 - For subjects treated with surgical stripping this is defined as absence of refluxing or residual vein and it will be collected at 30 days, 6 and 12 months only.
3. Technical success of each target vein immediately post-index procedure:
 - For subjects treated with the VenaSeal™ system or ETA this is defined as DUS showing vein closure along the entire treated vein segment with no discrete segments of patency exceeding 5 cm.
 - For subjects treated with surgical stripping this is defined as absence of refluxing or residual vein.
4. Reintervention of any target vein (including primary target vein) through 60 months, assessed at each follow-up visit (through 12 months for subjects enrolled in the VenaSeal vs. Surgical Stripping Study).
5. Time to reintervention of any target vein (including primary target vein) through 60 months, as measured by the time between the index procedure and the first reintervention procedure (through 12 months for subjects enrolled in the VenaSeal vs. Surgical Stripping Study).

Safety secondary endpoints

6. Adverse events (AEs) occurring in the target limb, evaluated from index procedure through 12 months:
 - Hypersensitivity to VenaSeal™ adhesive
 - Phlebitis
 - Granuloma

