10.1. Schedule of Events and Data Collection

An overview of all data collection requirements is given in **Table 6** and **Table 7** below. All subjects (in the Randomized Studies as well as the VLU Study) will follow the assessment schedule in Table 6, and VLU Study subjects will also follow the assessment schedule in Table 7, until healing per the CIP definition has occurred. Study-specific assessments may not occur until the ICF has been obtained, and only trained/delegated personnel may conduct study specific assessments. Subjects should return to the study site for their study visits; other local hospitals or clinics should not be used as an alternative.

Some study follow-up visits are not routine care. Routine care post-procedure differs from site to site. However, follow-up visits that are not routine care are not considered burdensome and/or invasive.

VENASEAL SPECTRUM Clinical Investigation Plan

MDT18034

Version 5.0

Page 52 of 164

Medtronic

Table 6: Schedule of Assessments – All Subjects

Data Collection Requirement	Screening	Baseline (<30 days before procedure)	Index Procedure (Day 0)	Day 7 (± 2 days)	Day 30 (± 7 days)	3+ Months Adjunctive Therapy (Optional)	6 Months (± 4 weeks)	12 Months ¹ (± 8 weeks)	24, 36, 48 and 60 Months (± 8 weeks)	Unscheduled ²
Informed Consent	X									
CEAP Clinical Classification (2004 and 2020)	X					X	X	X	X	
Randomization	X									
Demographics, Medical History		X								
Concomitant Medications		X	X							
rVCSS	X			X	X		X	X	X	X
Patient-Reported Symptoms		X		X	X		X	X		
EQ-5D-5L QoL		X			X		X	X	X	
AVVQ QoL	X				X		X	X	X	
SF-36 QoL	X				X		X	X		
VenousTSQ ³					X		X	X		
Duplex Ultrasound		X ⁴	X	X	X		X	X	X	X
Procedure-related Data & Outcome			X							
Physician Satisfaction with Procedure			X							
Patient-Reported Outcomes				X	X		X	X	X	
Reintervention Review				X	X		X	X	X	
Healthcare utilization				X	X		X	X	X	
Adjunctive Therapy Assessment						X	X	X	X	
Adverse Event Assessment			X	X	X	X	X	X	X	X
Device Deficiency Assessment			X							

¹ Subjects in VenaSeal vs. Surgical Stripping Study will be followed through 12 months only.

Medtronic Business Restricted

CONFIDENTIAL

056-F275, v B Clinical Investigation Plan Template

²AE assessments at unscheduled visits are required. Additional assessments are per investigator's discretion; see section 10.11 for additional detail

³VenousTSQe captured at 30 Days; VenousTSQs captured at 30 Days, 6 Months and 12 Months

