7.8	Interim Analyses.....	23
7.9	Evaluation of Objectives	23
7.10	Safety Evaluation.....	52
7.11	Health Outcomes Analyses	53
7.12	Changes to Planned Analysis.....	53
8.	Validation Requirements.....	54

9. References	54
10. Statistical Appendices.....	54

1. Version History

Version	Summary of Changes	Author(s)/Title
1.0	
 Not Applicable, New Document 	[name], Principal Statistician
2.0	
 Update to note that elimination of truncal reflux will be summarized without hypothesis testing for the VenaSeal vs. Surgical Stripping Study, due to halted enrollment in sections 4.1, 7.5 and 7.9. Updated study design consistent with CIP changes in sections 5.1, 5.2, 6.2 and 7.9.3 (halting of Venaseal vs. Surgical Stripping study enrollment and reducing follow-up to 12 months and reduction in sample size of the VLU study) Add note on handling of VenaSeal vs. Surgical Stripping study data collected beyond 12 months in section 7.1.1 Added the scoring algorithm for the VenousTSQe and VenousTSQs in section 7.9.1.1.4 Added test for superiority in non-inferiority is met in section 7.9.1.2.3 Document updated using new template. 	[name], Principal Statistician
3.0	
 Re-organized the document so that each study endpoint is enumerated and the corresponding hypothesis, endpoint definition, analysis methods and analysis population are provided Return-to-work endpoints, return-to-normal activities, anatomic closure endpoints all revised use a time-to-first-event analysis to allow for censoring and incorporation of unscheduled follow-up visits Reintervention and healthcare utilization endpoints are revised to use a rate-based calculation to allow for potential recurrent events and differences in follow-up time Updated scoring of the VenousTSQe and VenousTSQs based on the final recommendations 	[name], Distinguished Statistician

2. List of Abbreviations and Definitions of Terms

Abbreviation	Definition
AE	Adverse Event

Abbreviation	Definition
AVVQ	Aberdeen Varicose Vein Questionnaire
CEAP	Clinical, Etiological, Anatomical, and Pathophysiological Classification
CIP	Clinical Investigation Plan
CRF	Case Report Form
DUS	Duplex Ultrasound
DVT	Deep Vein Thrombosis
EGIT	Endovenous glue induced thrombosis
EHIT	Endovenous heat induced thrombosis
EQ-5D	EuroQoL 5 Dimensions Standardized Quality of Life Survey
EVLA	Endovenous Laser Ablation
ETA	Endovenous Thermal Ablation

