The rate of reintervention will be summarized by treatment arm in each study. The rate is calculated such that the numerator is the number of reinterventions and the denominator is the number of vein-years of follow-up. The amount of follow-up per person is defined as their date of exit or last known follow-up minus their date of index procedure. The vein-years is the amount of person-years times the number of target veins. A Poisson model will compare the rate of reintervention between treatment arms, using the number of reinterventions as the outcome and the person years of follow-up as an offset.

Determination of Subjects for Analysis

The reintervention analysis will consist of the ITT population.

5. Time to reintervention of any target vein (including primary target vein) through 60 months, as measured by the time between the index procedure and the first reintervention procedure. Subjects enrolled in the VenaSeal vs. Surgical Stripping Study will be followed through the 12 months visit only.

Hypothesis

The following hypothesis will be tested:

$H_0: S_A(t) = S_C(t)$

$H_a: S_A(t) \neq S_C(t)$

where $S_A(t)$ and $S_C(t)$ are the survival function estimates at time point t in the VenaSeal™ system arm and the ETA or surgical stripping arm, respectively. In the VenaSeal vs. Surgical Stripping Study, $t=12$ months and is otherwise $t=60$ months.

Endpoint Definition

A reintervention is a retreatment of any segment of any target vein in the target limb previously treated as part of the study at the index procedure.

Analysis Methods

The time to reintervention will be summarized by treatment arm in each study. Time to the first reintervention of any target vein by treatment will be presented with Kaplan-Meier estimation. Day zero is the date of the index procedure. The censoring time is the time to study exit, the later of either the last

contact date or the discontinuation date, or the time point for analysis, whichever comes first. A log-rank test will be used to compare arms.

Determination of Subjects for Analysis

The reintervention analysis will consist of the ITT population.

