The rate of reintervention will be summarized. The rate is calculated such that the numerator is the number of reinterventions and the denominator is the number of vein-years of follow-up. The amount of follow-up per person is defined as their date of exit or last known follow-up minus their date of index procedure. The vein-years is the amount of person-years times the number of target veins.

Determination of Subjects for Analysis

ITT population

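### Protocol 10.13 stops assessing reintervention at the first event, which contradicts the protocol's own schedule and cannot supply the recurrent-event rate that the SAP reports and tests

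*Protocol*

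**What the plan says.** **Collection.** Protocol 10.13 covers both reintervention and time to reintervention. It says they are "assessed at each follow-up visit (except 7 days) until reintervention occurs or the study ends". Other places differ:

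- Protocol 5.2.3, endpoint 4 (and the Synopsis): "Reintervention of any target vein (including primary target vein) through 60 months, assessed at each follow-up visit", with 12 months for the Stripping Study and no stop at a first event.
- Protocol Tables 1 and 6: the row "Reintervention Review" is marked at Day 7, Day 30, 6 months, 12 months and 24 to 60 months. No footnote ends it after an event.
- SAP 7.9.2.3 item 7 (VLU Study): reinterventions are assessed at every follow-up visit.
- Protocol 10.10: none of the itemised visit lists names a reintervention review. This applies to Day 7, Day 30, 6 to 36 months, 48/60 months and the 48/60-month remote list.

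**Analysis.** The SAP version history for 3.0 says the endpoint was "revised to use a rate-based calculation to allow for potential recurrent events and differences in follow-up time". In SAP 7.9.1.4 item 4, "the numerator is the number of reinterventions and the denominator is the number of vein-years of follow-up". Follow-up runs from the index procedure to exit or last known follow-up and is not cut at a reintervention. A Poisson model compares the arms. The VLU Study reports the same kind of rate descriptively. Item 5 of 7.9.1.4 separately analyses time to the first reintervention by Kaplan-Meier and log-rank.

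**The concern.** The rule in 10.13 suits a time-to-first-event endpoint. Applied to endpoint 4 it removes every reintervention after the first from the numerator, while the subject keeps adding exposure for up to 60 months. The result would be neither a recurrent-event rate, because repeats are missing, nor a first-event rate, because exposure should then end at the event. The SAP moved to a recurrent-event estimand, and the protocol sentence that says how long to keep asking does not support it.

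At stake are the reported rate in both Randomized Studies, its Poisson comparison, and the descriptive VLU rate. Follow-up is long, and repeats not asked about at the time become harder to recover later.

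**Working it through.** The plan gives no expected reintervention rate, power or sample size for this endpoint, so there is no figure to reproduce. The check has two parts.

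**1. The texts side by side.** On stopping, 10.13 ends assessment at the first event; endpoint 4, Tables 1 and 6 and the SAP do not. On Day 7, 10.13 excludes it; the tables mark it. No text sets an order of precedence. The contradiction is therefore certain. Whether repeats are actually lost depends on which text sites follow and on what the CRF records, which the documents do not show.

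**2. Size if 10.13 is followed.** Assumptions: one target vein per subject (so vein-years and person-years coincide), complete follow-up of T years, and a constant true rate λ per year between 0.01 and 0.10.

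- Independent repeats: observed rate ÷ true rate = (1 − exp(−λT)) ÷ (λT). For λ = 0.05 and T = 5, λT = 0.25 and (1 − 0.7788) ÷ 0.25 = 0.885.
- Clustered repeats (gamma frailty, variance θ): [1 − (1 + θλT)^(−1/θ)] ÷ (λT). For θ = 1 this is 1 ÷ (1 + λT), so λT = 0.25 gives 0.800.
- Apparent rate ratio when the true ratio is 0.5 and λ is the control rate, independent repeats: (1 − exp(−0.5λT)) ÷ (1 − exp(−λT)).

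| λ per year | 60 months, independent | True ratio 0.5 appears as | θ = 1 | θ = 3 | θ = 5 | 12 months, independent |
|---|---|---|---|---|---|---|
| 0.01 | 97.5% | 0.506 | 95.2% | 91.0% | 87.3% | 99.5% |
| 0.02 | 95.2% | 0.512 | 90.9% | 83.7% | 77.9% | 99.0% |
| 0.05 | 88.5% | 0.531 | 80.0% | 68.1% | 59.9% | 97.5% |
| 0.10 | 78.7% | 0.562 | 66.7% | 52.6% | 44.3% | 95.2% |

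The θ columns are for 60 months. The formulas depend only on λT, so 12 months at 0.10 has the same values as 60 months at 0.02, with or without clustering.

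**Direction of the ratio.** With counting stopped at the first event and equal follow-up, the observed ratio is the ratio of first-event risks, p_A ÷ p_C. With m repeats per first event, the true ratio is p_A(1 + m_A) ÷ [p_C(1 + m_C)]. Take risks of 5% and 10%, so the observed ratio is 0.50:

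- m = 0.2 in both arms: 0.060 ÷ 0.120 = 0.50; no shift.
- m = 0.1 and 0.5: 0.055 ÷ 0.150 = 0.37; the observed value lies closer to 1.
- m = 0.5 and 0.1: 0.075 ÷ 0.110 = 0.68; the observed value lies further from 1.

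**Check of the fallback.** If exposure ends at the first event, expected events are 1 − exp(−λT) and expected exposure is (1 − exp(−λT)) ÷ λ. Their quotient is λ, so under a constant rate the true rate is recovered.

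**The case against.** The strongest reply is that 10.13 stands alone. Endpoint 4, both schedule tables and the SAP keep the review at every visit, so sites working from the tables would record repeats. Healthcare utilization for the target limb is also collected at each follow-up visit, including remote ones, and DUS is done at in-person visits. This stands to the extent that undercounting is conditional, not shown. It does not settle the matter: nothing says the tables prevail, the SAP does not say it draws the count from utilization data, and 10.13 is the only narrative instruction on how long to keep asking.

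Three stronger readings are tempting, and the documents do not support them.

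- That the reported rate is too low as a matter of fact. This needs sites to follow 10.13 and repeats to occur.
- That the arm comparison is always pulled towards no difference. This holds when both arms share one event process with proportional rates, because the arm with the higher rate then has more repeats per first event. It fails when repeats per first event are equal, or higher in the arm with the lower rate.
- That in a subject with two target veins a reintervention on one ends assessment of the other. Section 10.13 speaks of a target vein, so the stop can also be read vein by vein.

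The stakes are also limited. The loss is small if reintervention is rare. As a rough guide only, since recanalization is not reintervention, protocol 4.1 gives 60-month freedom from recanalization of 91.4% and 85.2% in an earlier randomized trial. These correspond to −ln(0.914) ÷ 5 = 0.018 and −ln(0.852) ÷ 5 = 0.032 per year. A ratio of 0.032 ÷ 0.018 = 1.78 would appear as 0.148 ÷ 0.086 = 1.72 with independent repeats. The p-value is one of the secondary tests that SAP 7.9.1.3 leaves unadjusted for multiplicity.

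**Conclusion.** The contradiction is established: 10.13 conflicts with endpoint 4, Tables 1 and 6 and the SAP on the stopping rule, and with the tables on Day 7. As written, it cannot supply the recurrent-event rate in SAP 7.9.1.4 and 7.9.2.3. The bias is conditional. If sites follow 10.13 and repeats occur, the rate is understated. Under the assumed rates, the observed value over 5 years is about 97.5% to 79% of the truth with independent repeats, and lower with clustering. At 12 months in the Stripping Study it is 95% or more, again with independent repeats. The effect on the rate ratio has no fixed direction. The time-to-first-reintervention analysis is not touched by the stop at the first event. The point merits correction because a stated collection rule defeats a stated estimand, not because a large error has been shown.

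**What to change.** 1. In protocol 10.13, delete the Day 7 exception and the words that end assessment at the first reintervention. Every reintervention on any target vein, with its date and vein, is then recorded at each follow-up visit to study end, as Tables 1 and 6 already schedule (12 months for the Stripping Study).
2. Add reintervention review to all the visit lists in protocol 10.10, including the 48/60-month remote list. Adding it to the remote list alone would leave the in-person lists out of line with Table 6.
3. Confirm that the CRF captures repeat reinterventions after a first one.
4. Add a fallback to SAP 7.9.1.4 item 4 and 7.9.2.3 item 7. If repeats were not collected, then for all subjects in that analysis count first reinterventions only, end exposure at the first reintervention, and label the result a first-reintervention rate. It must apply to everyone in the analysis: cutting exposure only for subjects with unrecoverable data would mix two estimands. The fallback overlaps with the existing time-to-first analysis, but it would be correctly named.

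The cost is one sentence in 10.13, one line in each visit list, a CRF check and one SAP sentence per study type. No visit is added. The reported rate may rise slightly if repeats are found.

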10.14. Assessment of Safety

An AE assessment will take place at each follow-up visit (from the moment the index procedure is initiated until completion of follow-up or study exit). Reports of AEs and device deficiencies (refer to section 12) will be evaluated by Medtronic. The CEC will review and adjudicate events in accordance with section 13.1. Additional details are outlined in the CEC Charter.

